2.1 Objectives and Endpoints

Objectives	Endpoints
Primary	
• To describe the safety and tolerability of long-term administration of evolocumab	• Subject incidence of adverse events
Secondary	
• To describe the effects of long-term administration of evolocumab on low density lipoprotein cholesterol (LDL-C) levels • To describe the effects of long-term administration of evolocumab in subjects achieving an LDL-C level of < 40 mg/dL (1.03 mmol/L)	• Percent change of LDL-C from baseline at each scheduled visit • Achievement of an LDL-C level < 40 mg/dL (1.03 mmol/L) at each scheduled visit
Exploratory	
• To describe the effects of long-term administration on non-high-density lipoprotein cholesterol (non-HDL-C), apolipoprotein B (ApoB), total cholesterol, lipoprotein(a) (Lp[a]), triglycerides, high-density lipoprotein cholesterol (HDL-C), LDL-C, very low-density lipoprotein (VLDL-C), and apolipoprotein A1 (ApoA1) levels • To describe the effects of long-term administration of evolocumab on subject incidence of death and cardiovascular events of interest	• Change and percent change from baseline at each scheduled visit in each of the following lipid parameters: 
• non-HDL-C• ApoB• Total cholesterol• Lp(a)• Triglycerides• HDL-C• LDL-C• VLDL-C• ApoA1 
• Subject incidence of events positively reviewed by the CEC:
• All deaths• Cardiovascular events of interest:
○ Myocardial Infarction (MI)○ Stroke○ Coronary revascularization○ Hospitalization for unstable angina○ Hospitalization for heart failure○ Transient Ischemic Attack (TIA)

2.2 Hypotheses and/or Estimations

The primary clinical hypothesis is that long-term exposure of evolocumab will be safe and well tolerated in subjects with clinically evident atherosclerotic cardiovascular disease (CVD).

3. Study Overview

3.1 Study Design

This is a multicenter, open-label extension (OLE) study designed to assess the extended long-term safety of evolocumab in subjects who have completed the FOURIER trial (Study 20110118). FOURIER is a randomized placebo-controlled study of evolocumab, in patients with clinically evident atherosclerotic CVD on stable effective statin therapy. Subjects at sites participating in FOURIER OLE (Study 20160250) who are eligible and have signed the FOURIER OLE informed consent will be enrolled after completion of FOURIER.

The FOURIER OLE study requires laboratory assessments at day 1, week 12, and thereafter approximately every 6 months from day 1; the corresponding blood samples will be processed using a central laboratory.

Upon enrollment in FOURIER OLE study, subjects will receive evolocumab 140 mg every 2 weeks (Q2W) or 420 mg monthly (QM) according to their preference. Frequency and corresponding dose of administration can be changed at any scheduled time point where evolocumab is supplied to the subject, provided the appropriate supply is available. It is recommended that subjects continue the same background lipid-lowering therapy (LLT), including statin, as taken during FOURIER.

This study will continue for 260 weeks (approximately 5 years). Subjects ending administration of evolocumab should continue study assessments until the end of study.

All subjects will be followed and complete procedures/assessments from enrollment through the date of study termination unless the subject has withdrawn consent, irrespective of whether the subject is continuing to receive treatment. All deaths and cardiovascular events of interest will be reviewed by an independent external Clinical Events Committee (CEC), using standardized definitions.

3.2 Sample Size

It is estimated approximately 1600 subjects who completed the FOURIER trial will be enrolled. Based on sample size of 1600 subjects, [Table 3-1](#) lists the width of 95% confidence interval (CI) for a range of various underlying adverse event rates.

Table 3-1. Confidence Interval Width for Adverse Event Rates

Underlying Adverse Event Rate (%)	Width of 95% Confidence Interval
0.01	0.098
0.05	0.219
0.10	0.310
1.00	0.975
2.00	1.372
3.00	1.672
4.00	1.920
5.00	2.136

4. Covariates and Subgroups

4.1 Planned Covariates

Not applicable

4.2 Subgroups

The planned subgroups include the following:

- Baseline age (< 65 years, ≥ 65 years; < 75 years, ≥ 75 years)
- Sex (male, female)
- Race (white, non-white)
- Prior non-hemorrhagic stroke (yes, no)
- Symptomatic PAD (yes, no)
- Prior MI (No, < 1 year, 1 - < 2 years, ≥ 2 years)
- Baseline PCSK9 level (< median, ≥ median)
- Baseline LDL-C by quartiles (Q1, median, Q3)
- Baseline HDL-C by quartiles (Q1, median, Q3)
- Baseline triglycerides by quartiles (Q1, median, Q3)
- Baseline hsCRP (< 2 mg/L, ≥ 2 mg/L)
- Ezetimibe use at baseline (yes, no)
- ACC/AHA high statin background therapy intensity at baseline (yes, no)
- History of type 2 diabetes (yes, no)
- Heterozygous Familial Hypercholesterolemia (HeFH) at OLE enrollment (definite, probable, neither definite nor probable)
- **Subjects who were randomized to and received evolocumab group in the parent (i.e., FOURIER) study with ≥ 7 years of the combined exposure for evolocumab across the parent and OLE studies.**

5. Definitions

5.1 Study Time Points

Baseline

The baseline value is defined as the subject's baseline value from the parent study (FOURIER), unless otherwise specified.

First Dose Date of Investigational Product (IP)

For each subject, the first dose date of IP is the date of the first administration of evolocumab in **this OLE study**.

End of Investigational Product (EOIP) Date

For each subject, end of investigational product is the date reported on End of Investigational Product Administration eCRF.

Last Dose Date of Investigational Product

For each subject, the last dose date of investigational product is defined as the date of the last administration of investigational product (evolocumab or placebo).

If the last dose was administered in-clinic, then the Last IP Dose Date is the last start date captured on the IP Administration (In-Clinic) eCRF page.

If the last dose was administered at a non-investigator site location, then the Last IP Dose Date is defined as the final dose date reported by the subject on the Non-Clinic Final Investigational Product Dose Date eCRF page.

End of Study (EOS) Date

For each subject, the end of study date is defined as the last day that protocol-specified procedures are conducted for an individual subject, including safety follow-up and survival assessment. The EOS date is recorded on the End of Study eCRF.

Enrollment Date

The enrollment date for each subject is recorded on the Subject Enrollment eCRF **in the OLE study**.

Study Day 1

Study day 1 is defined as the day of the first administration of evolocumab in the study or the day of enrollment for subjects who are not administered any dose of evolocumab.

Study Day

For each subject, and for a given date of interest, study day is defined as the number of days since study day 1:

Study day = (date of interest – study day 1 date) + 1

If the date of interest is prior to the study day 1:

Study day = (date of interest – study day 1 date)

Study End Date

The study end date is the last EOS date of all enrolled subjects.

Categories of Time-to-first-event Endpoints

All time-to-first-event endpoints in this study are categorized below.

- **Composite**
 - **time to cardiovascular death, myocardial infarction, hospitalization for unstable angina, stroke, or coronary revascularization, whichever occurs first**
 - **time to cardiovascular death, myocardial infarction, or stroke, whichever occurs first**
 - **time to cardiovascular death or hospitalization for worsening heart failure, whichever occurs first**
 - **time to ischemic fatal or non-fatal stroke or transient ischemic attack, whichever occurs first**
 - **time to the first fatal and non-fatal myocardial infarction**
 - **time to the first fatal and non-fatal stroke**
- **Non-mortality**
 - **time to the first coronary revascularization**
- **Mortality**
 - **time to cardiovascular death**
 - **time to coronary death**
 - **time to death by any cause**

Censoring date

Endpoints are censored differently according to the endpoint categories. The censoring schema are described in below:

- censoring date for the composite and non-mortality endpoints is the EOS date in the OLE study.
- censoring (or time-to-event) for mortality endpoints are detained in appendix C.

Time-to-first-event Definition

- For the time-to-first-event analysis based on combined the parent and OLE data, the events adjudicated as positive in the parent study and occurred prior to or on subject last confirmed survival status date in the parent study (i.e., primary analysis in the parent study; please see the definition in the parent study SAP version 3.1 dated Aug 09, 2016) are included in addition to the events reviewed as positive in the OLE study (defined as below).

For the time-to-first-event analysis based on the OLE data only, mortality events reviewed as positive and occurred prior to or on later of (the EOS date or last known survival status date from eCRF page(s) in this OLE study) and non-mortality events reviewed as positive and occurred prior to or on the EOS date are included. For those subjects who already experience such event in the parent study, their time to event and censor flag are same as those in the parent study.

- For those subjects who didn't experience such event in the parent study, the derivation of the time-to-event and censoring date is presented below

For analyses combined both the parent and OLE studies		
Endpoint	Time-to-event for subjects with events	Censoring date for subjects without events
Composite or Non-mortality	First event onset date reviewed by CEC in OLE study – randomization date in the parent study +1	EOS date in OLE study

Mortality	Death endpoint date reviewed by CEC in OLE study – randomization date in the parent study +1	For subjects who died not due to death endpoint, the censoring date is the death date (reviewed by CEC) in OLE study For remaining subjects, the censoring date is max (EOS date, last known survival status date from eCRF page(s)) in the OLE study
For analyses based on OLE data only		
Composite or Non-mortality	First event onset date reviewed by CEC in OLE – enrolment date in OLE study +1	EOS date in OLE study
Mortality	Death endpoint date reviewed by CEC in OLE study – enrolment date in OLE study +1	For subjects who died not due to death endpoint, the censoring date is the death date (reviewed by CEC) in OLE study For remaining subjects, the censoring date is max (EOS date, last known survival status date from eCRF page(s)) in the OLE study

Patient-years of follow-up for treatment emergent adverse events

For analyses based on combined both the parent and OLE studies:

- 1) Subjects had first event in parent study: date (first event) – date (first dose date in FOURIER) + 1
- 2) Subjects had first event in OLE: study exposure in parent study + (date (first event) – first dose date in OLE + 1)
- 3) Subjects didn't have events: study exposure in parent study + (min [date (EOS in OLE), date (last dose date in OLE)+30] – first dose date in OLE + 1)

For analyses based on OLE study:

- 1) Subjects had events: date (first event in OLE) – date (first dose date in OLE) + 1

2) Subjects didn't have events: min [date (EOS in OLE), date (last dose date in OLE)+30] – date (first dose date in OLE) + 1

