7.2.2 Treatment

The following procedures will be completed during the 5-year (260 week) treatment period at the times designated in the Schedule of Assessments ([Table 3](#)).

Administration of evolocumab is to be administered after completion of the blood draws and vital signs during each visit that it is required.

- vital signs (eg, sitting blood pressure and heart rate)
- review of adverse events/serious adverse events/adverse device effects/disease-related events
- review of concomitant therapy
- body weight
- **coronary revascularization procedure and death information (sites will be prompted for this information when necessary)**
- blood draws for fasting lipids (\geq 9-hour fasting sample), ApoA1, ApoB, and Lp(a)
- blood draw for a serum pregnancy test (women of childbearing potential only by central laboratory per local institutional standard practice)
- administration of evolocumab at study site (see [Section 6.2.1](#) for instruction and supervision of subjects), if applicable
- reconciliation of used evolocumab, and dispensing evolocumab (prefilled AI/pens or PIs), if applicable

The investigator should instruct the subject to report to the site (eg, by telephone call) any adverse events, serious adverse events, adverse device effects, disease-related events at any time (ie, between scheduled visits). In addition, subjects will be contacted by telephone as designated in the schedule of assessments ([Table 3](#)) for collection of adverse events, serious adverse events, adverse device effects, disease-related events.

If, in the opinion of the investigator, a subject is unable to tolerate evolocumab, that subject will discontinue evolocumab but will continue to return for all other study procedures and measurements through the EOS.

If a subject withdraws from the study early, investigators should make every effort to complete and report the observations as thoroughly as possible up to the date of withdrawal. If possible, the **week 260** procedures should be completed at the time of withdrawal (see [Section 7.2.3](#)).

Vital status must be obtained for all subjects within the limits of local law. This includes subjects who may have discontinued study visits with or without withdrawing consent and should include interrogation of public databases, if necessary. If deceased, the date of death should be obtained and reported.

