8.4 Lost to Follow-up

A subject will be considered lost to follow-up at the end of the study if he or she repeatedly fails to return for scheduled visits and is unable to be contacted by the study site.

The site must attempt to contact the subject at each scheduled visit and reschedule the missed visit as soon as possible and counsel the subject on the importance of maintaining the assigned visit schedule and ascertain whether or not the subject wishes to and/or is able to continue in the study. These contact attempts are to be documented in the subject's medical record.

For subjects who are lost to follow-up, the investigator (or vendors approved by the site) can search publicly available records as permitted by applicable law to ascertain survival status. This ensures that the data set(s) produced as an outcome of the study is/are as comprehensive as possible.

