		
in definition for Enrollment date and Study day 1.
 
10. Added Categories of Time to first-event Endpoints with definitions and derivations in section 5.1
 
11. Rationale – To incorporate the last known survival status information when censoring for mortality endpoints especially for those lost to follow up patients or patients that withdrew consent.
 
12. Updated derivation for patient years of follow up for TEAE. Rationale – To count parent study and OLE period as two distinct periods which are added together, rather than 1 period from parent study's first dose to end of OLE
 
13. Update IP and Study Exposure Derivation for the combined parent and OLE study period. Rationale – To only sum of the two separate study exposure from the parent study and OLE studies (i.e., excluding the gap time between end of parent study and start of OLE) instead of the continuous study exposure from start of parent study till end of OLE (i.e., including the gap time between end of parent study and start of OLE).
 
14. Update section 8.3.2 to include imputation methods for handling partial dates of the CEC reviewed events and death events. Rationale: To be consistent with Fourier reporting.
 
15. Update the wording of the primary endpoint in Table 9-1 Rationale: This change is to clarify that all events listed are treatment emergent
 
16. Updated section 9.3 to include COVID-19 related protocol deviations and important protocol deviations Rationale: Per GDE-409220, the COVID-19 related PD and IPD will also be summarized and listed as per Amgen standard
 
17. Update the language in section 9.5.1 Analyses of Primary Endpoint Rationale: To clarify that all adverse event summaries will include not only Clinical Events Committee (CEC) reviewed events but also disease related events; to clarify that disease related events will be coded with

--	--	--

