8.3.2 Handling of Missing Data

Missing and partially missing dates will be queried. Partial/missing EOS dates will be imputed as the maximum of (last dose date of IP, vital signs assessments, lab assessments, AE start dates, concomitant medication start dates and imputed EOS date if partially missing). Partial/missing onset dates (reviewed by CEC) of

time-to- first-event endpoints will be imputed using the following algorithm, with the reference date being the enrollment date.

- Impute the missing year as the year of the reference date
- Impute the missing month as January
- Impute the missing day as 1st

Partial/missing start dates of adverse events and disease-related adverse events will be imputed using the following algorithm, with the reference date being the first dose date.

- Impute the missing year as the year of the reference date
- Impute the missing month as January
- Impute the missing day as 1st

If any of the resulting dates are prior to the reference date, the imputed date will be reset to the reference date. Please note for completely missing start dates of adverse-events and disease-related adverse where 'Did event start before first dose of investigational product?' on eCRF is recorded as 'Yes' will not be imputed. In addition, any imputed death dates will be the maximum of (the all adverse event start dates [use imputed event dates if missing], subject EOS dates [use imputed EOS dates if missing], and subject last confirmed survival status date recorded on the survival status eCRF page). For CEC death events and AE death event start dates, missing or partial missing dates will use the imputed death dates.

Adverse events with a valid answer to the question 'Did event start before first dose of investigational product?' on eCRF can be well defined based on the answer regardless of dates being completely or partially missing. Adverse events that cannot be determined as prior to IP or not either by the question above or by the onset date will be counted as treatment-emergent adverse events.

Concomitant medication with completely or partially missing start dates will be queried. After the query is resolved and the date is still incomplete with year only or year and month only, the start date will be imputed as described in [Table 8-1](#) below.

Table 8-1. Imputation Rules for Incomplete Dates

	Missing	Imputation	Exception
--	---------	------------	-----------

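### The SAP's end-of-study date can be set by a survival check, yet it censors composite and non-fatal endpoints, so time without event ascertainment may count as event-free

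*SAP*

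**What the plan says.** **EOS date.** SAP 5.1 (End of Study Date) defines it as the "last day that protocol-specified procedures are conducted for an individual subject, including safety follow-up and survival assessment". It is recorded on the End of Study eCRF.

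**Composite and non-mortality endpoints.** SAP 5.1 (Censoring date) states that the "censoring date for the composite and non-mortality endpoints is the EOS date in the OLE study". The table there applies this to the OLE-only and the combined analyses. For OLE-only analyses the event window ends on the same date: "non-mortality events reviewed as positive and occurred prior to or on the EOS date are included".

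**Mortality endpoints.** For subjects still alive, "the censoring date is max (EOS date, last known survival status date from eCRF page(s)) in the OLE study". The Amendment 2 entry in the SAP's summary of changes gives the reason: "To incorporate the last known survival status information when censoring for mortality endpoints especially for those lost to follow up patients".

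**Missing EOS date.** SAP 8.3.2: "Partial/missing EOS dates will be imputed as the maximum of (last dose date of IP, vital signs assessments, lab assessments, AE start dates", followed by concomitant medication start dates. Survival status is not in the list.

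**Follow-up after visits stop.** Protocol 7.2.2: "Vital status must be obtained for all subjects within the limits of local law", including subjects who have discontinued visits, with public databases if necessary. Protocol 8.1 says that subjects who stop treatment and assessments should not be removed from the study automatically. Protocol 8.4: "A subject will be considered lost to follow-up at the end of the study if he or she repeatedly fails to return" and cannot be contacted. Protocol 8.4 and 12.4 allow searches of public records for survival status.

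The SAP defines no date of last non-fatal event ascertainment.

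**The concern.** A vital-status check shows whether a subject is alive. It does not show whether the subject has had a myocardial infarction, stroke or revascularization. If such a check sets the EOS date, the subject remains in the risk set for those events from the last real event review up to the check, and can contribute no non-fatal event in between. For example, a subject who stops visits in year 2 and is found alive in year 5 could be censored at year 5 as free of non-fatal events.

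The error runs one way: incidence is too low. The outputs at stake are the exploratory summaries of positively reviewed events in SAP 9.5.3, namely the yearly Kaplan-Meier estimates and possibly the exposure-adjusted rates. These are shown by parent randomized group, so unequal stopping between the groups would also distort that display.

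**Working it through.** **1. The plan's own figure.** The only computed design figure is the confidence interval width in SAP Table 3-1. Width = 2 × 1.96 × √(p(1−p)/1600) reproduces all eight rows; for example p = 1% gives 0.975 and p = 5% gives 2.136. It does not depend on the EOS definition.

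**2. Can a survival check set the date?** By the SAP 5.1 definition, yes: survival assessment is named among the procedures that count. The protocol makes it a required activity after visits stop. For a completer the problem does not arise, because the EOS call in Protocol 7.2.3 reviews adverse and disease-related events and coronary revascularization.

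**3. Is the SAP consistent with itself?** The mortality rule takes the later of EOS and last survival-status date. It adds something only if survival status can be later than EOS, which implies that EOS is meant to be the last study contact. The imputation list in 8.3.2 points the same way. The EOS definition does not. The same subject could therefore be censored late if EOS is recorded from a survival check, and early if EOS is missing and imputed.

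**4. Which denominators?** Follow-up for treatment-emergent adverse events in event-free subjects is min(EOS, last dose + 30 days), so a late EOS has essentially no effect there. SAP 5.1 defines patient-years for those events only. OLE study exposure in 5.3 runs to EOS. If the rates of committee-reviewed events use that exposure, they are affected. The Kaplan-Meier estimates are affected either way.

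**5. Illustrative size.** The event rate λ, the affected fraction f and the tail length t are assumptions; the documents give none of them. Both models assume five years of follow-up and no events found in the tail.

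*Fixed tail.* A fraction f has the last t years survival-only.
- Observed 5-year incidence under EOS censoring: E = (1−f)(1−e^(−5λ)) + f(1−e^(−(5−t)λ))
- Ascertained time per subject: E/λ
- Unascertained time added: f·t·e^(−(5−t)λ)
- Rate under EOS censoring: E divided by the sum of the two times

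With λ = 0.04 the true 5-year incidence is 1 − e^(−0.2) = 18.1%.

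| f | t (years) | 5-year K-M | Rate per 100 PY | Relative error |
|---|---|---|---|---|
| 0 | any | 18.1% | 4.00 | 0 |
| 2% | 1 | 18.1% | 3.98 | −0.4% |
| 5% | 2 | 17.8% | 3.92 | −2.0% |
| 10% | 3 | 17.1% | 3.76 | −6.1% |

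Last row: E = 0.9 × 0.1813 + 0.1 × 0.0769 = 0.1708; E/λ = 4.271; added time = 0.1 × 3 × 0.923 = 0.277; rate = 0.1708/4.548 = 0.0376. With λ = 0.02 the relative errors are the same to within 0.1 percentage point.

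*Uniform stopping.* Visits stop at a time uniform on 0 to 5 years in a fraction f, with λ = 0.03. The true 5-year incidence is 1 − e^(−0.15) = 13.9%. In the affected group the observed incidence is 1 − 0.1393/0.15 = 7.1%, and the mean added time is (5/λ − 0.1393/λ²)/5 = 2.38 years.

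| f | 5-year K-M | Added PY (N = 1600) | Total PY | Relative error in rate |
|---|---|---|---|---|
| 5% | 13.6% | 190 | 7,438 | −2.6% |
| 10% | 13.3% | 381 | 7,447 | −5.1% |
| 15% | 12.9% | 571 | 7,457 | −7.7% |

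**6. Composites.** All six composites in SAP 5.1 have a fatal component: cardiovascular death in three, fatal stroke or fatal myocardial infarction in the other three. A survival check can reveal deaths. If 30% or 50% of events are deaths that are still found (an assumption), the rate shortfalls in the second table shrink to 1.8%, 3.5% and 5.3%, or to 1.2%, 2.5% and 3.7%.

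**The case against.** The strongest reply is that the SAP already separates the two dates. EOS has its own eCRF page and survival status has another. The survival-status date enters only the mortality rule, and it was added for lost and withdrawn subjects. The imputation rule also treats EOS as last study contact. This stands as evidence of intent. It does not cure the rule, because the EOS definition that actually governs non-fatal censoring names survival assessment.

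A second reply concerns ascertainment. A reader might infer that nobody asks about events once visits stop. The documents do not support that. Protocol 8.1 requires discussion of follow-up by telephone or mail, through family, through treating physicians or from medical records. Protocol 8.4 requires a contact attempt at each scheduled visit. Some of the tail may be well ascertained, so assuming no events found there is the unfavourable extreme.

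Third, when loss to follow-up is declared is a matter of classification. It does not show that sites enter the date of a late database search as EOS. How sites complete that page cannot be seen here.

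Fourth, the outputs are exploratory, in a study with no planned inference. That limits the importance of the point but does not remove it.

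**Conclusion.** The point holds as a fault in the written rule. Followed literally, SAP 5.1 can count time without non-fatal event ascertainment as event-free, and this conflicts with the SAP's own handling of survival information. The bias is downward. It affects the exploratory Kaplan-Meier estimates of committee-reviewed events, and the rates if their denominators run to EOS.

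The size cannot be computed from the documents. It is zero if no subject has a survival-only EOS date. It is roughly 0.4% to 8% relative on the rate if 2% to 15% of subjects do, with no events found in the tail, and less for composites that include deaths. A reader might conclude that the reported incidence will be understated by several percent. That goes too far, because the affected fraction, the tail length and the lack of ascertainment are all assumed.

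The primary adverse event analysis is essentially unaffected.

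**What to change.** - State in SAP 5.1 that a survival-only contact does not set the censoring date for composite and non-mortality endpoints.
- Censor those endpoints at the last date on which non-fatal events were ascertained, capped at EOS. A visit, a telephone contact or a medical-record review counts if it covered adverse and disease-related events.
- Apply the same cut-off to the non-fatal events that are counted. Otherwise events found later by record search would count while event-free subjects are censored earlier, which biases incidence upward. For the same reason, state how a composite treats a cardiovascular death after the cut-off.
- Keep the later of EOS and last survival-status date for mortality endpoints.
- Report how many subjects have a survival-only date after the cut-off, by parent group, and state the denominator for the rates of committee-reviewed events.

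The cost is one derived date, slightly less person-time, and the exclusion from the main estimate of non-fatal events found after the cut-off, which can be listed. The sponsor should first confirm that contacts with a negative event review are dated in the database, since the schedule of assessments shows event review only as continuous.

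### Read literally, SAP 5.1 counts component-cause deaths after EOS in the composite endpoints but censors all other subjects at EOS, which biases the composite estimates upward, probably by a small amount

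*SAP*

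**What the plan says.** SAP 5.1 (Study Time Points) places the time-to-first-event endpoints in three categories: composite, non-mortality and mortality. Three of the six composites contain cardiovascular death, for example "time to cardiovascular death, myocardial infarction, or stroke, whichever occurs first". The other three contain fatal stroke or fatal MI.

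The rules that bear on the point are:

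- **Event inclusion, OLE data only, by type of event.** Deaths: "mortality events reviewed as positive and occurred prior to or on later of (the EOS date or last known survival status date". Non-fatal events: "non-mortality events reviewed as positive and occurred prior to or on the EOS date are included".
- **Censoring, by category of endpoint.** Composites and non-mortality endpoints: "censoring date for the composite and non-mortality endpoints is the EOS date in the OLE study". Mortality endpoints: "For remaining subjects, the censoring date is max (EOS date, last known survival status date from eCRF page(s)) in the OLE study".
- **Composite time to event, OLE data only.** "First event onset date reviewed by CEC in OLE – enrolment date in OLE study +1". This row does not limit the event date to EOS.
- **Combined parent and OLE analysis.** Parent-study events "are included in addition to the events reviewed as positive in the OLE study (defined as below", so the OLE inclusion rule carries over.

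SAP 9.5.3 plans subject incidence, exposure-adjusted rates and yearly Kaplan-Meier estimates for positively reviewed events. It also plans a sensitivity analysis of two of the composites that contain cardiovascular death.

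**The concern.** A subject's follow-up for an endpoint should end on a date that does not depend on whether the event happened. Suppose a subject's EOS date is at year 2 and survival is later traced to year 4. If the trace shows a positively reviewed cardiovascular death at year 4, the composite has an event at year 4. If it shows the subject alive, the composite is censored at year 2. Only subjects who die of a component cause keep their time after EOS.

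Late deaths therefore enter the numerator without the matching person-time of those who survived, and independent censoring fails. The Kaplan-Meier estimates and exposure-adjusted rates of the affected composites move upward.

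**Working it through.** **1. Set the two windows side by side.**

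| Endpoint | Deaths counted up to | Event-free subjects followed to | Match? |
|---|---|---|---|
| Mortality | later of EOS and last known survival status date | same date | yes |
| Non-mortality (coronary revascularization) | not a component | EOS | yes |
| Composite, fatal component | later of EOS and last known survival status date | EOS | no |
| Composite, non-fatal component | not applicable (non-fatal events to EOS) | EOS | yes |

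The mismatch is confined to the fatal components of composites. It reaches the three composites with cardiovascular death, and all six if fatal MI and fatal stroke are treated as mortality events.

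**2. Check that time after EOS can exist.** Protocol 7.2.2 requires vital status within the limits of local law, including for subjects who stop visits or withdraw consent. Under Protocol 8.4 the investigator "can search publicly available records as permitted by applicable law to ascertain survival status". The SAP's use of a maximum of the two dates implies that the survival date can be later than EOS.

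**3. The plan's own figure.** The plan gives no figure for this rule. Its only precision figures are the interval widths in SAP Table 3-1, which reproduce. For a 1% rate: 2 × 1.96 × √(0.01 × 0.99 / 1600) = 0.975 points. The point does not depend on them.

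**4. Rough size by hand.** From the documents: n = 1600 and 260 weeks, about 5 years. Assumed: 5% to 20% leave early, at 2.5 years on average, cardiovascular death occurs at 1% per year, and every late death is found and reviewed as positive.

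Late deaths = 1600 × proportion leaving × 2.5 × 0.01

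- 5%: 80 × 2.5 × 0.01 = 2
- 10%: 160 × 2.5 × 0.01 = 4
- 20%: 320 × 2.5 × 0.01 = 8

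**5. Simulation.** Each scenario used 2,000,000 subjects, scaled to 1600, over 260 × 7 / 365.25 = 4.98 years. Assumptions, none from the documents: cardiovascular death 0.5 to 1.5, non-fatal component events 2 and non-cardiovascular death 0.8 per 100 person-years; withdrawal unrelated to risk in 5% to 20% over the study; vital status and cause captured in 50% or 100% of those withdrawn. Person-time ran to first event or censoring, because SAP 5.1 defines patient-years only for treatment-emergent adverse events.

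True 5-year risk = 1 − exp(−(death rate + non-fatal rate) × 4.98). For 1.0 per 100 person-years this is 1 − exp(−0.03 × 4.983) = 13.89%.

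| CV death per 100 py | Withdrawn | Captured | True risk % | K-M %, events and censoring both cut at EOS | K-M %, as written | Difference (points) | Late deaths per 1600 |
|---|---|---|---|---|---|---|---|
| 0.5 | 5% | 50% | 11.71 | 11.71 | 11.73 | 0.03 | 0.5 |
| 1.0 | 5% | 100% | 13.89 | 13.85 | 13.96 | 0.11 | 1.8 |
| 1.0 | 10% | 100% | 13.89 | 13.90 | 14.13 | 0.23 | 3.7 |
| 1.0 | 20% | 100% | 13.89 | 13.89 | 14.39 | 0.50 | 7.4 |
| 1.5 | 20% | 100% | 16.00 | 16.02 | 16.75 | 0.74 | 11.2 |

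Differences come from unrounded values. The counts lie slightly below the hand figures, since some leavers have already had a first event or die of another cause. A common cut-off at EOS recovers the true risk to within simulation error. In the 10% row the event rate rises from 3.00 to 3.05 per 100 person-years, about 1.7%. Over all scenarios the relative rise runs from about 0.2% to 5%.

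**The case against.** **The phrase may have been meant more narrowly.** The derivation table groups composites with non-mortality endpoints, and only the mortality rows use the survival status date. The SAP's summary of changes says that the survival information was added for censoring mortality endpoints. On that view, mortality events means events of the mortality endpoints. This is fair evidence of intent, but the operative text does not say it. It also leaves the composites, a category of their own, with no stated event cut-off. Appendix C is cited for mortality endpoints only, so it cannot settle the composites. The sentence needs clarifying on either reading.

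**The gap after EOS may be short or rare.** SAP 5.1 defines EOS to include survival assessment, so a late survival check may itself move EOS. Protocol 8.1 says that stopping drug or visits should not automatically remove a subject, and Protocol 8.4 classes a subject as lost only at the end of the study. This stands. The gap arises mainly in withdrawn or lost subjects, not in everyone who stops treatment.

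**A late death also needs a positive cause.** Protocol 7.2.4.3.1 collects death information through EOS/safety follow-up or 30 (+3) days after the last dose, whichever is later. Beyond that, Protocol 7.2.2 and 8.4 secure survival status and date of death, not cause, and SAP Table 9-1 has a category for undetermined cause. This also stands and pulls towards the low end of the range.

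**The size is small against sampling error.** At 14% with n = 1600 the 95% interval is 2 × 1.96 × √(0.14 × 0.86 / 1600) = 3.4 points wide, against 0.23 points in the middle case. That is true, but the bias has a known direction and a larger sample would not remove it.

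**Conclusion.** The point holds on the text as written. For composites, deaths from a component cause that occur after EOS can count, while all other subjects stop at EOS. The direction is upward. The size is probably small: 0.03 to 0.74 points in the 5-year Kaplan-Meier estimate, with about 0.2 points and 4 deaths per 1600 in the middle case. All event, withdrawal and capture rates behind these figures are assumptions. The endpoints are exploratory and descriptive, and the primary endpoint has its own follow-up rule.

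Four stronger readings are tempting, and the documents do not support them:

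- A reader might infer that any death learned of after EOS is mishandled. A death that occurred by EOS but became known later is counted correctly.
- A reader might infer that every death after EOS extends follow-up. In a composite, only a positively reviewed component-cause death does.
- A reader might infer a distorted contrast between the parent-study groups. The same rule applies to both, and nothing in the documents shows unequal withdrawal or tracing.
- A reader might put the inflation near 1 point, with up to 15 extra events. That requires 20% leaving, full capture and a doubling of cardiovascular mortality after leaving (14.86% against 13.89%). The documents give no basis for the doubling.

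**What to change.** Add to SAP 5.1 that, for every composite endpoint, all components (including cardiovascular death, fatal MI and fatal stroke) count only if they occur on or before the composite's censoring date, the OLE EOS date. State that later deaths enter the mortality endpoints only, where event-free subjects are also followed to the survival status date. Apply the same sentence to the OLE-only and the combined analyses.

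The cost is one sentence and a matching change to the derivation. The downside is that a few late deaths will appear in the mortality endpoints but not in the composites, which a table footnote can explain.
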